### **8.1.4.2 Secondary Efficacy Variables for Induction Study**

Secondary efficacy variables are divided into two groups. The first group includes ranked secondary endpoints, which are ranked by clinical importance. Statistical significance is assessed at 0.050 (2-sided) in ranked endpoint order until the significant level exceeds

0.05. No additional statistically significant treatment differences could be declared after the first ranked endpoint fails to achieve 0.05. The second group includes all other additional secondary variables.

For categorical ranked and non-ranked secondary endpoints, the difference in proportions of subjects between treatment groups will be analyzed using the CMH test adjusted for stratification variables. Additionally, the two-sided 95% confidence interval for the difference in proportions will be provided. The non-responder imputation will be used for subjects with missing data at the endpoint evaluated. The last observation carried forward (LOCF) method will also be used as the sensitivity analyses for the primary and ranked secondary endpoints.

Change from Baseline in continuous ranked and non-ranked secondary endpoints will be analyzed using an ANCOVA model including factors of treatment and adjusting for the baseline values and the stratification variables. For analyses of changes from Baseline variables, both LOCF and OC analyses will be performed. The LOCF analysis is considered primary for inferential purposes. In addition, Mixed-Effect Model Repeated Measure (MMRM) will be applied, wherever appropriate, as a sensitivity analysis for the longitudinal continuous endpoints.

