Subjects assigned to the higher induction regimen will receive blinded adalimumab 160 mg at Baseline, Week 1, Week 2, and Week 3. At Week 4, subjects will receive 40 mg every other week (eow) through Week 12. Subjects assigned to the standard adalimumab induction regimen will receive blinded adalimumab 160 mg at Baseline and matching placebo at Week 1. Subjects will receive 80 mg and matching placebo at Week 2, and then matching placebo at Week 3. At Week 4, subjects will receive 40 mg every other week through Week 12.

At Week 12, subjects will be re-randomized in a 1:1 ratio to one of the two double-blinded exploratory treatment regimens (adalimumab clinically adjusted [CA] regimen and adalimumab therapeutic drug monitoring [TDM] regimen). The re-randomization at Week 12 will be stratified by induction treatment regimen, clinical response (CR-70) status at Week 12 and decrease in SES-CD $> 50\%$ from Baseline per the site investigator reading at Week 12. Among subjects achieving decrease in SES-CD $> 50\%$ from Baseline at Week 12, the randomization will be further stratified by achievement of an SES-CD ≤ 4 and at least a 2 point reduction versus Baseline and no subscore greater than 1 in any individual variable using the Week 12 SES-CD value provided by the site. No study drug will be administered or injected at the final visit.

Further details on the maintenance treatment regimen are provided in the protocol Section 5.1 Overall Study Design and Plan.

A schematic of the study design is presented in [Figure 1](#).

Figure 1. Study Schematic

Clinical evaluation will be at visits occurring at Baseline, Weeks 2, 4, 6, 8, 12, 14, 20, 26, 28, 34, 40, 42, 48, and 56/PD. An electronic diary will be dispensed at the Screening visit. In addition to routine physical examination, CDAI calculation, diary review, laboratory, adverse event, concomitant medication and vital sign assessments, the following will be collected:

- Results of study questionnaires (inflammatory bowel disease questionnaire [IBDQ], European Quality of Life 5 dimensions [EQ-5D], work productivity and impairment [WPAI]) at Baseline, Week 4, Week 8, Week 12, Week 26, Week 40 and Week 56/PD.
- Calculation of the SFPS at Baseline, Week 2, Week 4, Week 6, Week 8, Week 12, Week 14, Week 20, Week 26, Week 28, Week 34, Week 40, Week 42, Week 48 and Week 56/PD. The Screening results will serve as the Baseline value.

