4.3 Sample Size

The calculated Week 4 remission rate for higher dose regimen are based on the average of the PK-PD Linear model and E_{\max} model and is 56% $[(70\% [\text{Linear}] + 42\% [E_{\max}]) / 2]$ for infliximab naïve subjects and 45% $[(60\% [\text{Linear}] + 30\% [E_{\max}]) / 2]$ for infliximab experienced subjects. Assuming the ratio in the proposed study of infliximab naïve subjects versus infliximab experienced is 75% versus 25%, respectively, the weighted Week 4 remission rate will be approximately 50% for higher induction dose regimen. For the standard dose regimen, the Week 4 clinical remission rate will be approximately 30%. Subjects who meet all of the inclusion criteria and none of the exclusion criteria will be enrolled into the study and randomized in a 3:2 ratio at Baseline to receive a higher induction adalimumab regimen or standard induction adalimumab regimen during the double-blind period. A sample size of 500 (300 higher dose and 200 standard dose) will be adequate to detect at least a 20% treatment difference in clinical remission rates at Week 4 between the dosing regimens using Fisher's exact test with 99% power at a 0.05 two-sided significant level.

Since exposure/endoscopic relationships are not currently available for adalimumab, clinical remission will be based on PK/PD modeling which predicts an expected ~50% increase in the proportion of subjects with endoscopic response compared to the standard adalimumab induction regimen. The observed rate of endoscopic response (decrease > 50% SES-CD from Baseline [or for a Baseline SES-CD of 4, at least a 2 point reduction from Baseline]) in Study M05-769 was 44% at Week 12 with the currently approved dosing regimen. Thus, by extrapolation, the expected rate for the higher induction regimen is 66%. A sample size of 500 subjects (300 higher induction regimen and 200 standard induction regimen) will be adequate to detect at least a 22% treatment difference in endoscopic response (decrease > 50% SES-CD from Baseline [or for a Baseline SES-CD of 4, at least a 2 point reduction from Baseline]) rates at Week 12 between the dosing regimens using Fisher's exact test with approximately 99% power at a 0.05 two-sided significance level.

Since the clinical remission at Week 4 endpoint and the endoscopic response at Week 12 endpoint are likely not independent of each other, the power for the co-primary endpoints for the study is expected to be $> 98\%$.

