5.2 Variables Used for Stratification of Randomization

At Baseline, subjects will be randomized 3:2 to one of two double-blinded adalimumab Induction Study regimens (higher induction regimen or standard induction regimen). The randomization will be stratified by hs-CRP at Baseline (< 10 and ≥ 10 mg/L) using Screening hs-CRP values, prior infliximab use (Yes, No), Crohn's disease severity (CDAI ≤ 300 , > 300) at Baseline.

At Week 12, subjects will be re-randomized in a 1:1 ratio to one of two double-blinded exploratory treatment regimens (clinically adjusted [CA] regimen and adalimumab therapeutic drug monitoring [TDM] regimen). The re-randomization at Week 12 will be stratified by induction treatment regimen, clinical response (CR-70) status at Week 12, and decrease in SES-CD $> 50\%$ from Baseline per the site investigator reading at Week 12. Among subjects achieving decrease in SES-CD $> 50\%$ from Baseline at Week 12, the randomization will be further stratified by achievement of an SES-CD ≤ 4 and at least a 2 point reduction versus baseline and no subscore greater than 1 in any individual variable using the Week 12 SES-CD value provided by the site.

The randomization schedule will be prepared by the Statistics Department of AbbVie.

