10.0 Efficacy Analysis

10.1 General Considerations

All statistical tests will be two-sided with the significance level of 0.05. Descriptive statistics will be provided. These include the number of observations, mean, standard deviation, minimum, median, and maximum for continuous variables; and number and percent for discrete variables. The analysis will be performed using SAS[®] (SAS Institute Inc., Cary, NC, USA).

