10.3 Secondary Efficacy Analyses

For the analysis purpose, the secondary efficacy endpoints for the Induction Study are divided into two groups: (1) ranked secondary endpoints and (2) additional, non-ranked endpoints.

Ranked Secondary endpoints:

1. Proportion of subjects with sustained clinical remission (CDAI < 150) at both Weeks 4 and 12.

2. Proportion of subjects with CDAI < 150 at Week 4 and decrease in SES-CD > 50% from Baseline (or for a Baseline SES-CD of 4, at least a 2 point reduction from Baseline) at Week 12.
3. Proportion of subjects with clinical remission (CDAI < 150) at Week 12.
4. Proportion of subjects who discontinued corticosteroid use and achieved clinical remission (CDAI < 150) at Week 12 among subjects taking corticosteroids at Baseline.
5. Proportion of subjects with endoscopic remission (SES-CD \leq 4 and at least a 2 point reduction versus baseline and no subscore greater than 1 in any individual variable) at Week 12.
6. Change from Baseline in fecal calprotectin level at Week 4.
7. Proportion of subjects with hs-CRP < 5 mg/L and fecal calprotectin < 250 μ g/g at Week 4.
8. Proportion of subjects with CDAI < 150, hs-CRP < 5 mg/L, and fecal calprotectin < 250 μ g/g at Week 4.
9. Proportion of subjects with CDAI < 150, hs-CRP < 5 mg/L, SES-CD \leq 4 and at least a 2 point reduction versus baseline and no subscore greater than 1 in any individual variable, and fecal calprotectin < 250 μ g/g at Week 12.
10. Proportion of subjects who achieve an SES-CED \leq 2 at Week 12.
11. Proportion of subjects with clinical response (decrease in CDAI \geq 70 points from Baseline) at Week 4.
12. Proportion of subjects with clinical response (decrease in CDAI \geq 70 points from Baseline) at Week 12.
13. Proportion of subjects achieving response in IBDQ Bowel Symptom domain (increase of IBDQ bowel symptom domain score \geq 8) at Week 4.
14. Proportion of subjects achieving response in IBDQ Bowel Symptom domain (increase of IBDQ bowel symptom domain score \geq 8) at Week 12.

15. Proportion of subjects achieving response in IBDQ fatigue item (increase of IBDQ fatigue item score ≥ 1) at Week 12.

For these endpoints which are categorical variables, NRI method of imputation will be used for the missing values. LOCF will be used as a sensitivity analysis wherever applicable.

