Both LOCF and OC analyses will be performed for continuous endpoints. The LOCF analysis is considered primary for inferential purposes. In addition, Mixed-Effect Model Repeated Measure (MMRM) will be applied as a sensitivity analysis, wherever appropriate, for the longitudinal continuous endpoints.

For endoscopy related endpoints, there will be no LOCF imputation as there is only one post-baseline endoscopy during Induction. Only OC will be used as a sensitivity analysis.

The difference in proportions of subjects between treatment groups will be analyzed using the two-sided Cochran-Mantel-Haenszel (CMH) test adjusted for hs-CRP at Baseline (< 10 and ≥ 10 mg/L), prior infliximab use (or prior anti-TNF use for subjects randomized under original protocol), and Crohn's disease severity (CDAI ≤ 300 , > 300) at Baseline. Additionally, the CMH-based two-sided 95% confidence interval (CI) for the difference in the proportions between the treatment groups will be calculated. An exact CMH test will be used to handle zero cells.

The difference in change from Baseline between treatment groups will be analyzed using an ANCOVA model including factors of treatment, hs-CRP at Baseline, prior infliximab use (or prior anti-TNF use for subjects randomized under original protocol), and Crohn's disease severity at Baseline, and Baseline values. Parameter estimates with 95% confidence interval and *P*-value will be provided.

All additional efficacy endpoints will be non-ranked.

- Proportion of subjects with clinical response (decrease CDAI ≥ 70 points from Baseline) at each scheduled visit in Induction Study.

- Proportion of subjects with enhanced clinical response (decrease CDAI ≥ 100 points from Baseline) at each scheduled visit in Induction Study.
- Proportion of subjects who discontinue corticosteroid use at each scheduled visit in Induction Study among subject taking corticosteroids at Baseline.
- Proportion of subjects who achieve a composite subtotal score of SFPS < 50 at Week 12 who had an SFPS ≥ 100 at Baseline.
- Proportion of subjects who achieve a composite subtotal score of SFPS < 50 at Week 4 who had an SFPS ≥ 100 at Baseline.
- Proportion of subjects who achieve SES-CD ≤ 3 and at least a 2 point reduction versus baseline and no subscore greater than 1 in any individual variable at Week 12.
- Proportion of subjects with SES-CD = 0 at Week 12.
- Change from Baseline in fecal calprotectin level at each scheduled visit in Induction Study.

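### Ranked endpoints 13-15 are changes from Baseline in IBDQ scores, but the planned CMH test leaves out the Baseline score: valid, but less powerful than it could be

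*SAP*

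**What the plan says.** Induction SAP 10.3 lists 15 ranked secondary endpoints. Ranks 13 and 14 are bowel-domain response (increase of at least 8) at Weeks 4 and 12. Rank 15 is "Proportion of subjects achieving response in IBDQ fatigue item" (increase of at least 1) at Week 12.

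For every binary ranked endpoint the section specifies: "The difference in proportions of subjects between treatment groups will be analyzed using the two-sided Cochran-Mantel-Haenszel (CMH) test adjusted for hs-CRP at Baseline", with prior infliximab (or anti-TNF) use and CDAI up to or above 300 as the other two factors. Protocol 8.1.4.2 has the same rule: differences "between treatment groups will be analyzed using the CMH test adjusted for stratification variables". Missing outcomes count as non-response.

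Elsewhere the plan does adjust for Baseline:
- Continuous changes use ANCOVA with the Baseline value (10.3), and the MMRM in section 6.0 includes it.
- The non-ranked list in 10.3 includes change in the IBDQ total and domain scores, bowel among them, but not change in the fatigue item.
- The logistic regression with extra covariates in 10.2 covers the co-primaries only and does not name IBDQ.

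Section 4.2 schedules the IBDQ at Baseline and Weeks 4, 8 and 12, so the covariate exists.

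**The concern.** A responder defined by change from Baseline carries the Baseline score inside its definition. Low scorers have room to improve and tend to drift upward. A subject who starts at 7 on the 1-7 fatigue item cannot respond at all. Eligibility rests on CDAI and SES-CD, with no IBDQ threshold, so such subjects can be enrolled. For some other symptom endpoints the plan limits the problem by restricting on Baseline (SFPS of at least 100; stool frequency of at least 4.0 and/or abdominal pain of at least 2.0). The IBDQ responses have no such restriction, and the CDAI stratum is only an indirect proxy.

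Predictable variation between subjects therefore stays in the error term, and a chance imbalance in the starting score is corrected only so far as the strata capture it. At stake is some power on the last three endpoints of the hierarchy. The validity of the result is not at stake.

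**Working it through.** **Inputs from the documents.** "All statistical tests will be two-sided with the significance level of 0.05" (Induction SAP 10.1). Allocation: "randomized 3:2 to one of two double-blinded adalimumab Induction Study regimens" (5.2). Sample size 300 and 200 (4.3). Planning rates: 50% vs 30% for Week 4 remission, 66% vs 44% for Week 12 endoscopic response (4.3). No response rate, SD, correlation or power is given for ranks 13-15.

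**Step 1: reproduce the plan's own figures.** Section 4.3 sizes the Week 4 comparison "using Fisher's exact test with 99% power at a 0.05 two-sided significant level". With the normal approximation, power = Φ[(Δ − 1.96·SE0)/SE1], where SE0 is the pooled and SE1 the unpooled standard error.

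- 50% vs 30%: pooled rate (150 + 60)/500 = 0.42; SE0 = √(0.42·0.58·(1/300 + 1/200)) = 0.0451; SE1 = √(0.25/300 + 0.21/200) = 0.0434; (0.20 − 0.0883)/0.0434 = 2.57; power 99.5%. Fisher's exact test by full enumeration: 99.4%.
- 66% vs 44%: the same steps give 99.8%; Fisher's exact 99.8%.
- Product under independence: 0.9939 × 0.9978 = 0.992, consistent with the stated joint power above 98%.

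The stated figures reproduce. They leave no room for a useful gain on the co-primaries and say nothing about ranks 13-15. With 300 and 200 subjects and 40-50% response in the standard arm, 80% power corresponds to a difference of about 12.6 to 12.7 points.

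**Step 2: what adjustment can gain, by formula.** If the Baseline score explains a share R² of the outcome variance beyond the strata, the power of the adjusted test is about Φ[(1.96 + z_base)/√(1 − R²) − 1.96]. At 80% base power z_base = 0.842. For R² = 0.10: 2.802/0.9487 − 1.96 = 0.993, so power is 84.0%, a gain of 4.0 points. For R² = 0.05, 0.15 and 0.20 the gains are 2.0, 6.0 and 7.9 points.

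**Step 3: simulation of the planned test.** The 8-stratum CMH was compared with the Wald test of treatment in a logistic model with the three stratification factors and the continuous Baseline score. There were 300 and 200 subjects, with 10% missing counted as non-response. Assumed, not from the documents: bowel Baseline mean 40, SD 9; fatigue mean 3.3, SD 1.4; correlation between CDAI and IBDQ −0.5; 45% with hs-CRP of at least 10; 20% with prior infliximab; standard-arm response 40%, 50% or 60%. The effect was set so that the CMH had about 80% power (4,000 or 8,000 trials per setting).

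| Score | Baseline/follow-up correlation | CMH → adjusted, standard arm 50% | Gain in points at 40% / 50% / 60% |
|---|---|---|---|
| Bowel | 0.3 | 79.5% → 86.1% | 6.9 / 6.6 / 5.1 |
| Bowel | 0.5 | 80.7% → 84.5% | 4.8 / 3.8 / 3.9 |
| Bowel | 0.7 | 77.5% → 81.2% | 3.1 / 3.7 / 2.6 |
| Fatigue | 0.3 | 79.3% → 85.3% | 6.6 / 6.0 / 5.1 |
| Fatigue | 0.5 | 77.6% → 83.1% | 5.5 / 5.4 / 3.7 |
| Fatigue | 0.7 | 81.6% → 84.0% | 3.2 / 2.4 / 2.8 |

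Gains were computed before rounding; the range is 2.4 to 6.9. At other base powers the gains were 3.2 to 8.5 points (about 60%), 1.5 to 4.5 (about 90%) and 0.8 to 1.0 (about 98.5%, correlations 0.3 and 0.5 only). Replacing the CMH by a logistic model without the Baseline score moved power by at most 0.8 points, so most of the gain comes from the covariate.

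The gain tends to fall as the correlation rises, because change then depends less on the start. With equal SDs the correlation of Baseline with change is −√((1 − ρ)/2), that is −0.59, −0.50 and −0.39 for ρ = 0.3, 0.5 and 0.7. In the non-null simulations the correlation of Baseline with the binary response was about −0.24 to −0.42; squared, 0.06 to 0.18, in line with step 2.

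**Step 4: type I error.** Under no effect (6,000 trials, correlation 0.5), CMH and adjusted test rejected in 5.0% and 4.9% for bowel, and 5.7% and 5.9% for fatigue. The simulation SE is √(0.05·0.95/6000) = 0.28 points. The fatigue rates are slightly above nominal for both tests, so they do not count against adjustment.

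**The case against.** The strongest reply is that nothing here is an error. The CMH is valid under randomisation, follows Protocol 8.1.4.2, matches the randomisation strata, gives the planned confidence interval for the risk difference directly, and keeps one method across the binary ranked endpoints. No power target for ranks 13-15 is missed, because none is stated. All of this stands. It limits the point to efficiency and shows that the CMH has real advantages.

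The reply also holds that the matter is partly covered already. For the bowel domain this is right: its change from Baseline gets a Baseline-adjusted ANCOVA at each visit, although non-ranked. For the fatigue item no Baseline-adjusted analysis is planned. Section 7.1 compares Baseline IBDQ score between arms but does not name the bowel domain or the fatigue item.

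Four stronger readings are tempting, and the documents do not support them:
- A reader might infer a fixed loss of power. Its size rests on assumed inputs.
- A reader might infer that the chance of a claim rises by the same amount. Under the fixed sequence in 10.4, ranks 13-15 count only after both co-primaries and ranks 1-12 succeed, so the gain in formal claims should be smaller. It cannot be computed from the documents.
- A reader might take these as the only patient-reported outcomes in the hierarchy. Three CDAI components come from the patient diary, and CDAI drives a co-primary and several ranked endpoints.
- A reader might suppose that chance imbalance makes the CMH invalid. It does not; step 4 shows no such problem.

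**Conclusion.** The point holds as a low-cost improvement. The planned test of ranks 13-15 ignores a collected covariate that is built into the outcome. Adding it raised power in every non-null scenario examined: by about 2 to 7 points on the individual test at 80% base power with correlations of 0.3 to 0.7, and by about 1 point near 98.5%. Type I error was essentially the same as for the CMH.

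The direction is robust across the scenarios; the size depends on IBDQ means, SDs, correlations and effects that the documents do not give. The case is strongest for the fatigue item, which has no Baseline-adjusted analysis in any form. The co-primaries and the validity of the planned analysis are unaffected.

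**What to change.** Before unblinding, amend Induction SAP 10.3 for ranks 13-15:

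1. Fit a logistic model with treatment, the three stratification factors as main effects, and the continuous Baseline value of the same score (bowel domain for 13 and 14, fatigue item for 15).
2. Keep non-responder imputation for the outcome. State a rule that retains ITT subjects with a missing Baseline score, for example overall-mean imputation. The IBDQ is completed on paper, and without a rule such subjects would drop out of the model although the CMH keeps them as non-responders.
3. Report the standardised risk difference with a 95% CI, and take the p-value from the same estimate (delta method or robust variance) so that test and interval cannot disagree. The simulation tested the model coefficient, not this estimate.
4. Keep the CMH as sensitivity analysis. Record the change in Induction SAP 12.1, which now reports no differences from the protocol, because Protocol 8.1.4.2 names the CMH.

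If the protocol's main test is to stay, add the model as a pre-specified sensitivity analysis, as 10.2 does for the co-primaries.

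Cost: SAP text and one model per endpoint, with no new data. The downside of making it the main test is a method that differs from the other binary ranked endpoints and departs from the protocol wording.

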### **Stool Samples Collected**

#### **Fecal Calprotectin**

Fecal calprotectin will be performed for all subjects as indicated in [Table 3](#). If subjects are unable to provide a sample at the site visit, subjects will be sent home with a stool sample supply kit and the site will give instructions to assist with collection procedures. The fecal calprotectin sample collected during the Screening Period will be used as the

baseline. All stool samples should be collected before any bowel preparation for endoscopy is started and returned to the site within 3 days of collection.

The fecal calprotectin results will remain blinded to Investigator, study site personnel and the subject throughout the study.

The central laboratory will be utilized to process and provide results for these laboratory tests.

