4.4 Interim Analysis

An interim analysis of the primary endpoint and ranked secondary efficacy variables for the Induction Study only as well as safety data collected from Baseline through double-blind Week 12 may be performed after the last subject in ITT population completes the 12-week double-blind Induction Study. A database cut will be performed and any discrepant data will be clarified before the lock. Since this interim analysis is the only and final analysis of the co-primary efficacy endpoints of the Induction Study, multiplicity adjustment is deemed not necessary.

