10.4 Handling of Multiplicity

No adjustment for multiplicity will be done. In order to claim the study success, both co-primary endpoints need to be statistically significant at significance level 0.05 (two-sided). The co-primary endpoints will be tested prior to the ranked secondary endpoints; and the ranked secondary endpoints are tested for statistical significance only if both the co-primary endpoints meet statistical significance at a two-sided significance level of 0.05.

The statistical test for the ranked secondary endpoints will be carried out in the hierarchical order as specified in Section 10.3. This means that statistical significance for the remaining ranked secondary endpoints is assessed at 0.05 (2-sided) in the above order until the significance level exceeds 0.05. No additional statistically significant treatment differences could be declared after the ranked endpoint fails to achieve statistical significance at a two-sided significance level of 0.05.

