12.0 Summary of Changes

12.1 Summary of Changes Between the Latest Version of Protocol and the Current SAP

None.

12.2 Summary of Changes Between the Previous Version and the Current Version of the SAP

Under Section 6.0 Analysis Conventions: Only CD related systemic or rectal corticosteroids will be used for censoring purpose, and will have last non-missing value prior to censoring carried forward for non-categorical assessments) from that point forward. This change is made to be consistent with protocol Amendment 6.

In addition, SES-CD scoring rule is updated regarding missing individual variables. The missing SES-CD individual variables at Baseline will be imputed as 0. The post-Baseline missing SES-CD individual variables will be imputed as 0 if there are 8 or fewer missing individual variables. If more than 8 individual variables are missing, the total SES-CD will be missing for that visit. Both changes are based on newly created Analysis Convention for Crohn's Disease and Ulcerative Colitis Clinical Studies. The new imputation rule is also used by current Abbvie IBD registrational trials.

Bristol Stool Form Scale is not a continuous variable. The new variable Bristol Stool Chart score is defined as the number of days the subjects with Type 6 or Type 7 divided by the total number days with non-missing assessments, rounded to two decimal. If a subject achieved reduction from Baseline $\geq 50\%$, this subject will be classified as Bristol Stool Chart Responder. This change is made to be consistent with protocol Amendment 6.

The Week 12 visit window for SES-CD is updated so that no post-baseline Induction data will be discarded. In addition, endoscopy data collected prior to or within 7 days of the fist dose of maintenance study or OLE Study M14-347 will be considered for the Week 12 visit window for SES-CD; thus ensuring endoscopy data collected is not ignored

while also reflecting the efficacy based on the study treatment during the 12 week induction period.

Under Section 10.2, one of the co-primary endpoints, SES-CD ≤ 4 and at least a 2 point reduction versus baseline and no subscore greater than 1 in any individual variable) at Week 12 is replaced by decrease in SES-CD $> 50\%$ from Baseline (or for a Baseline SES-CD of 4, at least a 2 point reduction from Baseline) at Week 12. This change is made to be consistent with protocol Amendment 6.

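### Should the Week 4 change in fecal calprotectin (ranked secondary 6) be tested on the log scale, given that it gates nine later endpoints?

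*SAP*

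**What the plan says.** Endpoint 6 in the ranked list of the Induction SAP, Section 10.3, is "Change from Baseline in fecal calprotectin level at Week 4". The other 14 ranked endpoints are proportions. The same section gives one model for every change-from-Baseline variable: "The difference in change from Baseline between treatment groups will be analyzed using an ANCOVA model", with treatment, the three randomization stratification factors and the Baseline value as terms. Protocol Section 8.1.4.2 agrees: "Change from Baseline in continuous ranked and non-ranked secondary endpoints will be analyzed using an ANCOVA model including factors of treatment". LOCF is the primary missing-data approach for continuous endpoints. Observed-case and MMRM analyses are added.

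Neither document mentions a log or rank transformation, a non-parametric alternative or a check of distribution. That the analysis is on the raw scale is therefore inferred from silence.

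Induction SAP Section 10.4 sets the gate. Testing starts only after the co-primaries: "the ranked secondary endpoints are tested for statistical significance only if both the co-primary endpoints meet statistical significance". It then runs in fixed order: "No additional statistically significant treatment differences could be declared after the ranked endpoint fails to achieve statistical significance".

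**The concern.** A stool biomarker is a natural candidate for right skew. If its distribution is close to log-normal, a few large values dominate the raw-change residuals and the test loses efficiency. Such a loss on an unranked endpoint would hardly matter. Here a miss at endpoint 6 also blocks any claim of significance on nine further endpoints (7 to 15), if both co-primaries and endpoints 1 to 5 have succeeded. The observed-case and MMRM analyses use the same default scale, so no planned analysis would show the problem.

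A cheap remedy also seems available. Baseline calprotectin is a pre-treatment sample (the Protocol's Fecal Calprotectin section says "The fecal calprotectin sample collected during the Screening Period will be used as the" baseline), so its shape can be examined blind. This could be done before the Week 12 cut, about which Induction SAP Section 4.4 says "A database cut will be performed and any discrepant data will be clarified before the lock". The scale could then be fixed in the SAP and listed in Section 12.1, "Summary of Changes Between the Latest Version of Protocol and the Current SAP", which now records none.

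Two smaller points arise for the same endpoint. At Week 4 the primary LOCF analysis has no earlier value to carry forward. And it is not spelled out whether Baseline is carried for a subject censored for steroids before the first post-Baseline sample.

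**Working it through.** **The plan's own figures.** No power is stated for endpoint 6. The stated co-primary power does reproduce. With 300 against 200 subjects and a two-sided Fisher's exact test at 0.05, power is 99.4% for 50% against 30% and 99.8% for 66% against 44%. Under independence, joint power is 0.994 × 0.998 = 0.992, consistent with the stated figure of more than 98%.

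**Case 1: log-normal data, uniform percentage effect.** From the documents: 300 against 200 subjects, and ANCOVA on treatment, Baseline and three binary strata. Assumed: 10% missing (270 against 180), Baseline correlation 0.5, a 40% fall in the standard arm, and a further 25% lower geometric mean in the higher arm. Simulated power, 10,000 replicates per row:

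| log-SD | raw change | log change | loss (points) |
|---|---|---|---|
| 0.5 | 1.000 | 1.000 | 0 |
| 0.75 | 0.968 | 0.996 | 2.8 |
| 1.0 | 0.717 | 0.926 | 20.9 |
| 1.3 | 0.404 | 0.749 | 34.5 |
| 1.6 | 0.222 | 0.575 | 35.3 |

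The share of the sample that raw change retains is about ((1.96 + z_raw)/(1.96 + z_log))², where z is the normal quantile of the power. At log-SD 1.0 this is ((1.96 + 0.574)/(1.96 + 1.447))² = 0.55. At 1.3 it is ((1.96 − 0.243)/(1.96 + 0.671))² = 0.43.

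The loss depends on inputs that the documents do not give:

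- Effect size, at log-SD 1.0: a 15% effect gives 0.312 against 0.489 (17.7 points); a 40% effect gives 0.989 against 1.000 (1.1 points).
- Upper assay cap at 3 times the median: 0.840 against 0.926 at log-SD 1.0 (8.6 points), and 0.631 against 0.730 at 1.3 (9.9 points).
- A separate set of runs used 300 against 200, a standard-arm Week 4 ratio of 0.45, and an effect set so that log-scale power is 80% or 90%. The loss ran from 5 to 12 points at log-SD 0.6 up to 43 to 52 points at 1.6. With values clipped at assumed assay limits (30–3000 or 30–6000 µg/g) it was 12 to 25 points.

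**Case 2: other shapes.** Raw against log: gamma shape 1, 0.916 against 0.768; gamma shape 2, 0.999 against 0.990; normal with CV 0.33 and an additive effect, 0.897 against 0.738. Here log is the weaker choice.

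**Case 3: the same log-normal Baseline, effect not uniform.** With log-SD 1.2, correlation 0.5 and 300 against 200:

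| where the extra effect falls | raw | log |
|---|---|---|
| high Week 4 values only | 98.2% | 63.5% |
| top third of Baseline only | 68.1% | 66.2% |
| lower half of Baseline only | 19.1% | 95.0% |

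The Baseline distribution is identical in all three rows, yet the better scale changes. Baseline shape cannot choose between them.

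**Case 4: a switching rule.** Suppose log is used when the skewness of pooled log Baseline lies within ±0.5, and raw otherwise. Take log-SD 1.0 and 270 against 180, and let treatment shrink only the part of the Week 4 value above the standard-arm median, by a factor of 0.6, 0.5 or 0.4. The rule chose log in every replicate. Raw power was 0.66, 0.88 and 0.97; power under the rule was 0.30, 0.47 and 0.66. The rule loses 36, 41 and 31 points.

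**Type I error.** Under the null, rejection rates were 0.038 to 0.056 on the raw scale and 0.048 to 0.051 on the log scale. Both are acceptable.

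**The two wording points.** Table 6 of the Induction SAP assigns every calprotectin sample from Rx Day 2 to Day 57 to Week 4, and LOCF rule 1 bars Baseline. LOCF and observed-case results at Week 4 therefore coincide apart from any effect of steroid censoring, and saying so would change no number. On censoring, LOCF rule 1 concerns missing post-Baseline values, whereas the observed-case text has values seen after censoring replaced by the last one before it. An analyst can apply both without conflict. The group is probably small, since Protocol Section 5.2.3.2 bars changes to Baseline steroid doses in the first 4 weeks except for toxicity.

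**The case for a change.** The strongest case for acting is that a gate before nine endpoints rests on a default scale that nobody defended, that log-normality with a proportional effect is a plausible model, and that naming a scale before unblinding costs a few sentences. The sponsor has also reconsidered a measurement scale in this same SAP version: the Bristol stool variable was redefined because it is not continuous.

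Much of this stands. The silence is real, the power loss under that model is correctly computed, and a sentence confirming the scale with a log-scale sensitivity analysis would do no harm. What does not stand is the step to a change in the gate test. The gain exists only under an assumed shape, spread and pattern of effect. The same Baseline with a different pattern reverses it by as much. A sensitivity analysis would leave the gate result as it is. Moving the primary analysis to logs replaces a mean difference in µg/g with a ratio of geometric means, a change of estimand for which the documents offer no clinical reason.

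**Conclusion.** No change follows. The planned ANCOVA on change is valid, pre-specified consistently in Protocol and SAP, and controls type I error. Against a log analysis it may lose anywhere from nothing to about 52 power points if calprotectin is log-normal with a uniform percentage effect. It may gain some 30 to 40 points if the effect is concentrated in high values. These figures rest on assumed spread, correlation, effect size and assay limits, none of which the documents supply. A blinded look at Baseline does not resolve the choice, and the switching rule can be clearly worse than the plan. The cost arises only if both co-primaries and endpoints 1 to 5 succeed. Statisticians could reasonably choose either scale. The LOCF remark changes no result, and the steroid-censoring detail concerns a probably small group that analysts can handle from the existing text.
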